6.2 IMPORTANT PROTOCOL DEVIATIONS

Data discrepancies and deviations from the CTP will be identified for all subjects enrolled (i.e. signed informed consent available) who did not fail during screening. A list of protocol deviations (e.g. deviations in drug administration, in blood sampling times, etc.) will be provided to be discussed at the Report Planning Meeting (RPM)/ database lock meeting (DBLM). At this meeting, it will be decided whether a discrepant data point can be used or whether it must be corrected in the clinical database. For definition of important protocol deviations (iPD), and for the process of identification of these, refer to the Boehringer Ingelheim (BI) SOP "Identify and Manage Important Protocol Deviations (iPD)" (2).

Important protocol deviation (iPD) categories are pre-specified in the iPD specification file (DV domain). IPDs will be identified no later than in the Report Planning Meeting, and the iPD categories will be updated as needed.

If any iPDs are identified, they are to be summarised into categories and will be captured in the iPD specification file (DV domain) and in the decision log. Both documents will be stored within the TMF in EDMS.

The iPDs will be summarized and listed in the CTR.

6.3 INTERCURRENT EVENTS

For the following intercurrent events in the MD part, the hypothetical strategy as defined in ICH E9(R1) (13) will be applied for all ophthalmological efficacy endpoints (see [Table 5.3: 1](#)), i.e. data obtained after the intercurrent event will be censored and not included in the statistical analyses:

- Treatment discontinuation
- Administration of any anti-VEGF treatment in study eye or any intravitreal/intraocular steroid treatment other than the randomised treatment, if administration occurred during the trial

Censoring will be applied to all efficacy endpoints of the study eye. The start date of censoring is 28 days after treatment discontinuation or 1 day after start of a relevant concomitant medication (see definition above) in the study eye, whatever occurs first.

6.4 SUBJECT SETS ANALYSED

Enrolled set (ES)

This subject set includes all patients who were enrolled in the study regardless of whether they were treated or not. The ES is used for the disposition table / listing and the disclosure tables for enrolment.

Section 7.3 of the CTP:

Treated set (TS)

For part A the treated set includes all subjects who were treated with at least one dose of study drug.

For part B the treated set includes all subjects who were randomized and treated with at least one dose of study drug (either treatment with BI 765128 or Sham).

Analyses regarding safety and efficacy will be performed on the TS. For ophthalmological efficacy analysis, intercurrent events have to be taken into account respectively (see [Section 6.3](#)). For FAZ area, a supplementary analysis including all available data irrespective of intercurrent events (i.e. following the treatment policy approach as defined in ICH E9(R1)) will be performed in addition. The analysis population for the outputs of this analysis will be labelled “TS (supplementary analysis including data after intercurrent events)”.

Section 7.3 of the CTP:

Table 6.4: 1 Subject sets analysed

Class of endpoint	Subject sets		
	ES	TS	PKS
Analysis of ophthalmological endpoints		X	
Analysis of safety endpoints (incl. ECG)		X	
[REDACTED]			X
[REDACTED]		X	
Disposition / Disclosure of enrolment	X		
Demographic/baseline parameter		X	
Important protocol deviations		X	
Exposure		X	

[REDACTED]

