2.1.3 Secondary endpoint(s)

Part A:

- Number of subjects with drug related AEs at EOS
- Number of subjects with any ocular AEs (eye disorders) at EOS

Part B:

- Change from baseline of the size of the FAZ in optical coherence tomography angiography (OCTA) at visit 5
- Change from baseline of the size of the FAZ in optical coherence tomography angiography (OCTA) at visit 6
- Change from baseline of the size of the FAZ in optical coherence tomography angiography (OCTA) at visit 7
- Change from baseline of BCVA at Visit 7
- Number of subjects with any ocular AEs (eye disorders) from drug administration until EOS

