3.3.4.1 Discontinuation of trial treatment

An individual subject will discontinue trial treatment if:

1. The subject wants to discontinue trial treatment, without the need to justify the decision.
2. The subject has repeatedly shown to be non-compliant with important trial procedures and, in the opinion of both, the investigator and sponsor representative, is not willing or able to adhere to the trial requirements in the future.
3. The subject needs to take concomitant medication that interferes with the investigational medicinal product or other trial treatment.
4. The subject can no longer receive trial treatment for medical reasons (such as surgery, adverse events, other diseases, or pregnancy). An AE or clinically significant laboratory change or abnormality occurs that the investigator judge to warranting discontinuation of treatment

If new efficacy/safety information becomes available, Boehringer Ingelheim will review the benefit-risk-assessment and, if needed, pause or discontinue the trial treatment for all subjects or take any other appropriate action to guarantee the safety of the trial subjects.

Even if the trial treatment is discontinued (Part B), the subjects remain in the trial and, given their agreement, will undergo the procedures for early treatment discontinuation and follow-up as outlined in the [Flow Chart II](#) and section [6.2.3](#).

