5.2 ASSESSMENT OF SAFETY

5.2.1 Dose limiting event

A DLE is defined as the occurrence of any of the following events in the study eye within the evaluation period (7 days after drug administration):

- Development of sterile endophthalmitis and/or sterile inflammation of the vitreous of grade 3+ according to the NEI Grading of vitreous haze, and anterior chamber cells of 3+ according to the Standardization of Uveitis Nomenclature (SUN) working group (WG) grading scheme (see Table 5.2.1: 1 below) and a duration of 5 or more days between day 1 and day 8
- Visual loss of more than 15 letters at any given time-point
- Persistent IOP over 30 mmHg for 3 days
- Signs of vascular occlusion in a 1st (the main branch) or 2nd degree (the vessel after the first bifurcation of the main branch) retinal vessel, including peripheral retinal hemorrhages in the area supplied by the occluded vessel (hemorrhage of the macula would not be included as this is a symptom of the disease)

Table 5.2.1: 1 The SUN Working Group Grading Scheme ([R18-1136](#))

Grade	Cells in Field ¹
0	0
0.5+	1-5
1+	6-15
2+	16-25
3+	26-50
4+	>50

¹ Field size is a 1 mm by 1 mm slit beam.

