7.5.2 Secondary objective analysis

Section 7.3.3 of the CTP:

The secondary endpoints (refer to [Section 5.2.2](#)) will be summarized by means of descriptive statistics (at least n, mean, standard deviation, median, minimum and maximum) for continuous variables or frequency tables for categorical variables. (...)

Analyses regarding safety and efficacy will be performed on the TS.

Model-based analyses will be performed for all ophthalmological efficacy endpoints of the MD part that were defined as secondary endpoints, i.e. FAZ area and BCVA. These analyses will only be done for the study eye and not for the fellow eye.

The change from baseline in the respective secondary endpoint will be analysed via a restricted maximum likelihood (REML) based approach using a mixed model with repeated measurements (MMRM).

The model will include the fixed, categorical effects of treatment at each visit and the fixed continuous effects of baseline at each visit. Visit will be treated as the repeated measure with an unstructured covariance structure used to model the within-patient measurements.

The statistical model will be as follows

$$y_{ijk} = \beta_j S_i + \tau_{jk} + e_{ij}$$

$$e_{ij} \sim N_Z(\mathbf{0}, \Sigma).$$

y_{ijk} = response variable (as change from baseline) for subject i at visit j receiving treatment k ,

S_i = the baseline measurement of subject i , $i=1,2,\dots$

β_j = coefficient of baseline effect at visit j

τ_{jk} = the effect of treatment k at visit j , $j=1,\dots,Z$ and $k = 1, \dots, Y$,

e_{ij} = the random error associated with the j^{th} visit of the i^{th} subject. Errors are independent between subjects.

Σ = an unstructured covariance matrix

The Kenward-Roger approximation will be used to estimate denominator degrees of freedom and adjust standard errors. Least-squares means per treatment and for the treatment difference will be provided by time point, and in addition corresponding two-sided 95% confidence intervals and p-values will be presented.

The following SAS code can be used to fit the model:

```
PROC MIXED DATA=indata CL METHOD=REML;
CLASS subject treat visit;
MODEL endpoint = baseline treat visit treat*visit baseline*visit/ DDFM=KR
CL
ALPHA=0.1;
REPEATED visit / SUBJECT=subject TYPE=UN;
LSMEANS treat*visit/ DIFF CL ALPHA=0.1 SLICE=visit;
RUN;
```

In the event of non-convergence, the following methods will be attempted (in order) to overcome it:

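### BCVA has no treatment-policy analysis, so observed Visit 6–7 BCVA after treatment discontinuation is unused and a lasting treatment-caused vision loss is under-represented at Visit 7

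*SAP*

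**What the plan says.** SAP 6.3 applies a hypothetical strategy to the ophthalmological efficacy endpoints of Part B, so that "data obtained after the intercurrent event will be censored and not included in the statistical analyses". The triggers are treatment discontinuation and certain anti-VEGF or steroid treatments. The scope is broad: "Censoring will be applied to all efficacy endpoints of the study eye". The timing is: "The start date of censoring is 28 days after treatment discontinuation or 1 day after start of a relevant concomitant medication", whichever comes first.

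BCVA falls under this rule. SAP 7.5.2 models the ophthalmological endpoints "defined as secondary endpoints, i.e. FAZ area and BCVA", and Protocol 2.1.3 gives BCVA a single time point: "Change from baseline of BCVA at Visit 7".

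SAP 6.4 adds a treatment-policy analysis, but the sentence begins "For FAZ area, a supplementary analysis including all available data irrespective of intercurrent events"; BCVA is not named. SAP section 4 drops the LOCF sensitivity analysis that the protocol had planned.

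Protocol 3.3.4.1 includes adverse events among the reasons for stopping: "The subject can no longer receive trial treatment for medical reasons (such as surgery, adverse events, other diseases, or pregnancy". The same section keeps Part B subjects in the trial after stopping, if they agree, and Protocol 6.2.3 asks for their end-of-study visit.

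**The concern.** The trial's objective is safety and tolerability, and loss of vision is one of its toxicity criteria: Protocol 5.2.1 lists "Visual loss of more than 15 letters at any given time-point" as a dose limiting event. If a subject stops because of an adverse event and vision stays reduced, the later BCVA readings show whether the harm lasted. These readings should be collected, but the censoring rule removes them from the BCVA analysis.

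For FAZ area the plan shows both pictures, with and without data after the intercurrent event. For BCVA it shows only the hypothetical one, which asks what vision would have been without the event. When the drug itself causes the event, that question sets part of the harm aside. At stake is a Visit 7 BCVA difference that looks more favourable to active treatment than the observed data would.

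**Working it through.** The documents give no BCVA standard deviation, effect size or discontinuation rate, so there is no planned figure to reproduce. The check has two parts.

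**1. Which visits are lost (dates from the Protocol flow chart for Part B and SAP Table 6.7: 3).** Injections are at Visits 2, 3 and 4 (Days 1, 29, 57).

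- Stop decided at Visit 3: 29 + 28 = Day 57. Visit 3 is kept, Visit 4 (planned Day 57) is borderline, Visits 5–7 are out.
- Stop decided at Visit 4: 57 + 28 = Day 85. Visits 3–4 are kept, Visit 5 (planned Day 85) is borderline, Visits 6–7 are out.
- Latest case inside the protocol window: 57 + 3 + 28 = Day 88. With Visit 4 at the end of its extended SAP window: 71 + 28 = Day 99.
- The extended window for Visit 6 opens on Day 100 and for Visit 7 on Day 128.

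So Visits 6 and 7 are excluded for every subject who discontinues treatment. The visible text does not say whether the discontinuation date is the last dose or the decision. If it is the last dose, a subject dosed only on Day 1 is censored from Day 29, and even Visit 3 is borderline.

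**2. How much of a lasting loss survives at Visit 7.** The arm sizes of 20 and 10 are from Protocol 4.1.3. Assumed: SD of BCVA change 6 letters, equal correlation r of 0.5 or 0.8 between visits, and a permanent loss in one or two active subjects.

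Shift in the all-data Visit 7 active mean = -(subjects × letters lost)/20:

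- one subject losing 30 letters: -30/20 = -1.5
- two losing 15 each: -30/20 = -1.5
- two losing 30 each: -60/20 = -3.0

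In the planned repeated-measures model, a censored subject's retained values predict the missing ones. With m retained visits and equal correlation, each gets the regression weight r/(1 + (m - 1)r). If the loss is visible at q of them, the share of the shift kept at Visit 7 is q·r/(1 + (m - 1)r). The table sets this beside a simulation: 100 replicates per setting, maximum likelihood, unstructured covariance, Visits 3–7, no baseline covariate. The ranges cover the three loss patterns above.

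| Loss seen from | Visits kept | q, m | Formula, r = 0.5 | Simulated | Formula, r = 0.8 | Simulated |
|---|---|---|---|---|---|---|
| Visit 3 | 3 | 1, 1 | 0.5 = 50% | 46–51% | 0.8 = 80% | 79–81% |
| Visit 3 | 3–4 | 2, 2 | 1/1.5 = 67% | 67–71% | 1.6/1.8 = 89% | 88–92% |
| Visit 4 | 3–4 | 1, 2 | 0.5/1.5 = 33% | 31–37% | 0.8/1.8 = 44% | 42–45% |
| Visit 4 | 3–5 | 2, 3 | 1/2 = 50% | 48–54% | 1.6/2.6 = 62% | 59–62% |
| after censoring | 3–4 | 0, 2 | 0% | -2 to 2% | 0% | -1 to 2% |

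In letters, when the loss is measured before censoring:

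- Of the -1.5 shift, the model shows between -0.47 and -1.38, so it omits 0.12 to 1.03.
- Of the -3.0 shift, it shows between -1.11 and -2.63, so it omits 0.37 to 1.89.

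When the loss first appears after censoring, essentially the whole shift is omitted.

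**The case against.** A reader might infer that a treatment-caused loss would be missing from every BCVA comparison and that the planned analysis would show no effect. The documents do not support this. The 28-day lag normally keeps the reading taken around the event that led to stopping. SAP 7.5.2 reports differences at each time point, and its unstructured covariance carries a subject's own low values forward instead of assigning the arm mean. A loss that first appears after censoring cannot have caused the stop. A loss after all three injections is not a treatment discontinuation, so it stays in unless a censoring treatment is given. All of this stands, and it limits the size of the effect.

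Nor is the harm hidden from the trial. Protocol 5.1 has clinically significant worsening reported as an adverse event. SAP 6.1 counts events up to trial termination with no 28-day rule. SAP 7.8.1 tabulates drug-related and study-eye ocular events, and SAP section 7 lists individual values of all subjects. This also stands. However, tables and listings give no between-arm estimate of BCVA, and event entry depends on the investigator's judgement.

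A BCVA mean is also a weak detector of one or two cases. With an assumed SD of 5 to 10 letters, the unadjusted standard error is SD × √(1/20 + 1/10) = SD × 0.387, or 1.9 to 3.9 letters. A -1.5 shift is then 0.4 to 0.8 standard errors. That is correct, but it argues for modest expectations and does not justify leaving out observed data.

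Finally, Part B is sized on FAZ and is exploratory, which may explain reserving the supplement for FAZ. Parts of the SAP, including Table 5.3: 1, are not in the public text, so another BCVA summary cannot be ruled out.

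**Conclusion.** The point holds in a limited form. On the visible text, BCVA has no treatment-policy analysis, and the observed Visit 6–7 values of subjects who discontinue enter no planned BCVA comparison. A lasting treatment-caused loss is therefore attenuated at Visit 7 when it is measured before censoring (roughly 31% to 92% of the shift kept), and absent when it first appears afterwards. The second case could arise if a subject stops for another adverse event and vision falls later, or if an intraocular steroid or anti-VEGF treatment triggers the 1-day rule, which can also apply after all three injections.

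The percentages rest on the assumed correlation, the simplified model and the chosen loss patterns; the SD matters little for the share kept. The date arithmetic rests on the documents alone. The gain from a change is modest, but the change needs no new data and removes an asymmetry between the two modelled secondary endpoints.

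**What to change.** In SAP 6.4, extend the supplementary analysis from FAZ area to FAZ area and BCVA. Run the same treatment-policy repeated-measures model and descriptive table for BCVA, under the output label already defined for FAZ. In SAP 6.3, it would help to add one sentence saying whether the discontinuation date is the last dose or the decision to stop, because this decides which visits are kept.

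The cost is a short SAP edit, one repeat of existing code and one extra set of outputs. The main hypothetical analysis is unchanged, and the follow-up that supplies the data is already scheduled.

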6.6 HANDLING OF MISSING DATA AND OUTLIERS

Handling of missing data and outliers will be performed as described in the CTP, Section 7.4.

Section 7.4 of the CTP:

Safety

Missing baseline laboratory values will be imputed by the respective values from the screening visit. No other imputations will be performed on missing data although every effort will be made to obtain complete information on all AEs, with particular emphasis on potential DLEs.

[REDACTED]

[REDACTED]

[REDACTED]

Efficacy

All data will be analyzed and presented without any form of imputation.

Missing time at unscheduled ocular assessments performed on the day of administration are regarded as on treatment. The missing time will be imputed and set to 23:59 at the day of administration.

Missing or incomplete AE dates are imputed according to BI standards (see BI-KMED-BDS-HTG-0035) (3).

Missing data and outliers of PK data are handled according to BI standards (see BI-KMED-TMCP-HTG-0025 (4) and BI-KMED-TMCP-MAN-0014 (5)).

ECG analysis

If single cardiac cycles of an ECG (out of the generally four) are missing, the arithmetic mean for this single ECG will be computed with the reduced (1, 2 or 3) number of cardiac cycles.

If replicate ECG recordings are missing, the arithmetic means per time point will be computed with the reduced number (1 or 2) of recordings.

For the classification of the on-treatment QTc/QT intervals into “no new onset” / “new onset” categories, the handling of missing values is described in Additional [Section 10.1.2](#).

6.7 BASELINE, TIME WINDOWS AND CALCULATED VISITS

Section 5.1 of the CTP:

For the endpoints, baseline is defined as the value at Visit 2; if not measured at Visit 2 then baseline is the value at Visit 1.

Baseline is defined as the last measurement before first administration of trial medication.

Section 6.1 of the CTP:

The acceptable time windows for visits are given in the CTP Flow Charts. For planned individual serum concentration sampling times, refer to CTP appendix 10.1.

Analysis of AE data, potentially clinically significant abnormal laboratory values, concomitant medication or non-drug therapies, as well as use of rescue therapy will not be based on visits. Therefore, no assignment to time windows will be necessary for such data.

All other safety and efficacy measurements will be assigned to visits based on extended time windows around the planned visit dates, defined relative to the day of first trial treatment (which is scheduled for Visit 2). These extended time windows are defined in [Table 6.7: 1](#) to [Table 6.7: 5](#).

Only one observation per time window will be selected for statistical analysis at a particular visit – the value which is closest to the protocol planned visit day will be selected, except for safety lab and ████ where the worst scenario is chosen (i.e. for IOP the highest value will be taken). If there are two observations which have the same difference in days to the planned day, the later value will be selected. If there is more than one IOP measurement being the worst value within a time window, the value collected closer to the planned day will be selected.

Proprietary confidential information © 2023 Boehringer Ingelheim International GmbH or one or more of its affiliated companies.

Table 6.7: 1 Time window assignment of efficacy, safety lab, ████, vital signs and weight measurements to visits for statistical analysis of the SRD Part

Visit (CTP)	Week	Visit label (analysis)	Planned Day	Time window [days]		
				Window per CTP	Start (extended)	End (extended)
V2	Baseline	Baseline	1	± 0	NA	1
V3*		Day 4 (FU)	4	± 1	2	6
V4*	Week 1	Day 8 (FU)	8	± 2	7	11
V5	Week 2	Day 15 (FU)	15	± 2	12	22
V6	Week 4	Day 29 (FU)	29	± 3	23	43
V7	Week 8	Day 57 (FU)	57	± 7	44	78
V8	Week 14/EOS	Day 99 (EOS)	99	± 7	79	End of Trial visit date

* Safety lab is not scheduled for Day 4. Consequently, the time window for Day 8 is [2, 11], the other time windows remain the same.

Table 6.7: 2 Time window assignment of 12 lead ECG measurements to visits for statistical analysis of the SRD Part

Visit (CTP)	Week	Visit label (analysis)	Planned Day	Time window [days]		
				Window per CTP	Start (extended)	End (extended)
V2	Baseline	Baseline	1	± 0	NA	1
V3		Day 4 (FU)	4	± 1	2	16
V6	Week 4	Day 29 (FU)	29	± 3	17	43
V7	Week 8	Day 57 (FU)	57	± 7	44	78
V8	Week 14/EOS	Day 99 (EOS)	99	± 7	79	End of Trial visit date

Days are counted relative to the day of first treatment, which is defined as Day 1.

Table 6.7: 3 Time window assignment of efficacy, safety lab, ████ and vital signs measurements to visits for statistical analysis of the MD Part

Visit (CTP)	Week	Visit label (analysis)	Planned Day	Time window [days]		
				Window per CTP	Start (extended)	End (extended)
V2	Baseline	Baseline	1	± 0	NA	1
V3	Week 4	Day 29	29	± 3	2	43
V4	Week 8	Day 57	57	± 3	44	71

Visit (CTP)	Week	Visit label (analysis)	Planned Day	Time window [days]		
				Window per CTP	Start (extended)	End (extended)
V5	Week 12	Day 85 (FU)	85	± 7	72	99
V6	Week 16	Day 113 (FU)	113	± 7	100	127
V7	Week 20/EOS	Day 141 (EOS)	141	± 7	128	End of Trial visit date

Table 6.7: 4 Time window assignment of 12 lead ECG measurements to visits for statistical analysis of the MD Part

Visit (CTP)	Week	Visit label (analysis)	Planned Day	Time window [days]		
				Window per CTP	Start (extended)	End (extended)
V2	Baseline	Baseline	1	± 0	NA	1
V3	Week 4	Day 29	29	± 3	2	43
V4	Week 8	Day 57	57	± 3	44	71
V5	Week 12	Day 85 (FU)	85	± 7	72	End of Trial visit date

Days are counted relative to the day of first treatment, which is defined as Day 1.

Table 6.7: 5 Time window assignment of physical examination measurements (weight) to visits for statistical analysis of the MD Part

Visit (CTP)	Week	Visit label (analysis)	Planned Day	Time window [days]		
				Window per CTP	Start (extended)	End (extended)
V2	Baseline	Baseline	-28 to -3	NA	NA	1
V5	Week 12	Day 85 (FU)	85	± 7	2	End of Trial visit date

Days are counted relative to the day of first treatment, which is defined as Day 1.

Section 5.2.5.1 of the CTP:

Central ECG lab evaluation will be performed for all ECGs indicated in the CTP Flow Chart I and CTP Flow Chart II. For all ECGs this will include the intervals RR, PR, QRS and QT measured semi-automatically. The screening ECGs will be checked for abnormalities.

At all time points mentioned in the CTP Flow Charts, single ECGs will be recorded shortly before the PK sampling at the respective time points, and will be transferred to the central ECG lab.

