mode of administration	Not applicable
Duration of treatment	
Part A: single intravitreal dose
 
Part B: 3 intravitreal doses at [REDACTED] [REDACTED]

Statistical methods	The main objectives of this trial will be assessed by calculating descriptive statistics on DLEs and drug related AEs. For the Part B these will be compared descriptively between the treatment groups.

	The dose escalation in the SRD part will be guided by a Bayesian logistic regression model (BLRM) with overdose control that will be fitted to binary toxicity outcomes. The estimates of parameters will be updated as data are accumulated using the BLRM.
--	--

FLOW CHART I (PART A)

Trial Periods	Screening Period	Treatment Visit	Follow-up period					End of study
			3	4	5	6	7	
Visit	1	2	3	4	5	6	7	8
Study Days	Duration 3 to 28 days	Day 1	4	8	15	29	57	99
Study Weeks				Week 1	Week 2	Week 4	Week 8	Week 14
Time window for visits (days)		none	±1	±2	±2	±3	±7	±7
Informed consent	X							
Demographics	X							
Medical history	X							
Physical examination (including weight)	X	X ⁽¹⁾				X	X	X
Vital signs	X	X	X	X	X	X	X	X
Laboratory tests	X	X		X	X	X	X	X
12-lead ECG ⁽²⁾	X	X	X			X	X	X
Review of in-/exclusion criteria	X	X						
Dose Assignment		X						
IVT drug administration		X						
Pregnancy test ⁽³⁾	X _S	X _S		X _U	X _U	X _U	X _U	X _U
PK 								
 sampling ⁽⁴⁾		X			X	X	X	X
BCVA testing	X	X	X	X	X	X	X	X
SD-OCT	X	X	X	X	X	X	X	X
OCT Angiography	X	X	X	X	X	X	X	X
Fundus Photo	X	X		X	X	X	X	X
Slit lamp and intra-ocular pressure (IOP)	X	X	X	X	X	X	X	X
All AEs/SAEs/AESIs	X	X	X	X	X	X	X	X
Concomitant therapy	X	X	X	X	X	X	X	X
Completion of subject participation ⁽⁵⁾								X

(1) Could be repeated as deemed necessary at investigator's discretion.

(2) Single ECGs are to be recorded shortly before the PK sampling at the respective time points, (Section 5.2.5. and Appendix 10.1).

Proprietary confidential information © 2023 Boehringer Ingelheim International GmbH or one or more of its affiliated companies

- (³) Pregnancy testing: serum pregnancy test (X_S) is done at screening and on day 1 if more than a week elapsed between screening and day 1, and at the other visits as a reflex when urine testing (X_U) is positive.
- (⁴) 
- (⁵) Completion of subject participation also needs to be completed in the eCRF if the subject withdraws prematurely following assignment to dose level (Section [3.3.4](#))

FLOW CHART II (PART B)

Trial Periods	Screening Period	Treatment Period			Follow-up Period		End of Study

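### SAP Table 6.7:1 assigns a protocol-compliant Part A Visit 4 on Day 6 to Visit 3, which leaves Day 8 empty in the by-visit summaries

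*SAP*

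**What the plan says.** Protocol Flow Chart I (Part A), in the row "Time window for visits (days"), gives Visit 3 as Day 4 ±1 and Visit 4 as Day 8 ±2.

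SAP section 6.7 does not analyse by nominal visit: "All other safety and efficacy measurements will be assigned to visits based on extended time windows around the planned visit dates". Table 6.7:1 prints the protocol tolerance and the analysis window side by side. For Visit 3 it gives ±1 and Days 2-6. For Visit 4 it gives ±2 and Days 7-11.

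Within a window, "Only one observation per time window will be selected for statistical analysis at a particular visit", and in general "the value which is closest to the protocol planned visit day will be selected". If two values are equally close, the later one is used. The exception is safety lab and one blacked-out item, "where the worst scenario is chosen (i.e. for IOP the highest value will be taken").

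Two provisions limit the reach of these rules:
- A footnote to Table 6.7:1 covers safety lab: "Safety lab is not scheduled for Day 4. Consequently, the time window for Day 8 is [2, 11], the other time windows remain the same".
- For adverse events, potentially clinically significant laboratory values, concomitant medication and rescue therapy, section 6.7 says: "Therefore, no assignment to time windows will be necessary for such data".

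**The concern.** SAP section 4 announces analysis windows wider than those of the protocol. At its lower end the Visit 4 window is narrower: Day 6 is allowed by the protocol but lies outside the Visit 4 row and inside the Visit 3 row. A subject who keeps to the schedule can therefore lose the Day 8 value for every windowed measurement except safety lab.

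BCVA, SD-OCT, OCTA, IOP and vital signs are scheduled at both visits, so all are exposed. Part A cohorts have 3, 3 and 6 subjects (Protocol section 3.1). One missing value is a third of a 3-subject Day 8 summary, and a Day 6 IOP shown under Day 4 misstates when the pressure was measured.

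**Working it through.** **Inputs.** Visit tolerances are from Flow Chart I; analysis windows and selection rules are from SAP section 6.7.

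**1. Reproducing the printed windows.** The planned days are 4, 8, 15, 29, 57 and 99. The midpoints of neighbouring days are:
- (4+8)/2 = 6
- (8+15)/2 = 11.5
- (15+29)/2 = 22
- (29+57)/2 = 43
- (57+99)/2 = 78

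Giving each whole-day midpoint to the earlier visit yields window ends 6, 11, 22, 43 and 78, exactly as printed. The Day 6 boundary thus fits a general midpoint rule.

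**2. Compliant days against each visit's own window, Part A.**

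| Visit | Protocol days | SAP window | All inside? |
|---|---|---|---|
| 3 | 3-5 | 2-6 | yes |
| 4 | 6-10 | 7-11 | no, Day 6 falls in Visit 3 |
| 5 | 13-17 | 12-22 | yes |
| 6 | 26-32 | 23-43 | yes |
| 7 | 50-64 | 44-78 | yes |
| 8 | 92-106 | 79 to end | yes |

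The same check on the ECG windows (Tables 6.7:2 and 6.7:4) and the Part B windows (Table 6.7:3) finds no conflict. Part A Visit 4 on Day 6 is the only one.

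**3. What happens to the Day 6 value.**
- *Closest-day rule.* Day 6 is |6 − 4| = 2 days from Day 4; a compliant Visit 3 (Days 3, 4 or 5) is 0 or 1 day away. Visit 3 is always chosen and the Day 6 value is dropped. The later-value tie rule is not reached.
- *Visit 3 missing.* The Day 6 value is the only one in Days 2-6 and is labelled Day 4.
- *IOP, highest value taken.* A Day 6 reading above the Visit 3 reading is shown as Day 4; a lower one is dropped.
- *Safety lab.* Day 6 lies in [2, 11] and is correctly labelled Day 8.

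Except for safety lab, Day 8 has no value unless an unscheduled reading falls on Days 7-11. Of the 3 × 5 = 15 compliant combinations of Visit 3 and Visit 4 days, the 3 with Visit 4 on Day 6 leave Day 8 empty.

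**4. Possible size.** The documents do not say how often Visit 4 falls on Day 6. Let p be that chance, independent between subjects (assumption), with 3 + 3 + 6 = 12 Part A subjects. Expected losses are 12p. The chance that a 3-subject cohort loses at least one value is 1 − (1 − p)³.

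| p (assumed) | Expected of 12 | Cohort of 3 loses at least one |
|---|---|---|
| 5% | 0.6 | 1 − 0.95³ = 14% |
| 10% | 1.2 | 1 − 0.90³ = 27% |
| 20% | 2.4 | 1 − 0.80³ = 49% |

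The last row corresponds to visits spread evenly over the five allowed days.

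**The case against.** The strongest reply is that little depends on this table. The Part A primary endpoint is DLEs and its secondary endpoints are AE counts. AE data are not windowed, DLEs have their own 7-day table (SAP section 7.8.1), and dose escalation uses a review form completed after Visit 4 (Protocol section 3.1). The model-based analysis is for Part B only. SAP section 7 lists every subject's individual values, so a Day 6 reading remains in the report. All of this stands. A reader might infer that the DLE assessment is compromised because Visit 4 closes the 7-day period; the documents do not support that.

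It can also be said that Day 6 visits will be rare. Sites aim for Day 8, and the dose-escalation model counts a subject without a DLE only after at least 7 days of observation, which discourages an early visit. This is reasonable and makes the even-spread figure look high. It does not remove the conflict, because Flow Chart I still permits Day 6.

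A reader might go further and see a second gap on the dosing day. SAP section 6.6 states "Missing time at unscheduled ocular assessments performed on the day of administration are regarded as on treatment", yet the first post-baseline window opens on Day 2, so such a reading belongs to no visit. The documents do not show this to be a defect. Scheduled ophthalmic assessments precede the injection (Protocol section 6.2.2), baseline is the last value before first dosing, and nothing promises an unscheduled reading a place in the by-visit tables. Opening the window on Day 1 would do harm: under the highest-value rule, a raised post-injection IOP could be shown as Day 4 in Part A or Day 29 in Part B.

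**Conclusion.** The point holds for one boundary. A Part A Visit 4 on Day 6 complies with the protocol, yet Table 6.7:1 treats it as Visit 3, and no rule in the visible text returns it to Visit 4. The consequence is missing or mislabelled Day 4 and Day 8 entries for BCVA, SD-OCT, OCTA, IOP and vital signs in Part A descriptive summaries and plots. DLE and AE endpoints, safety lab, individual listings and Part B are untouched.

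The existence of the conflict rests on printed figures alone. Its size rests on an assumption: the range of 0.6 to 2.4 of 12 subjects comes from an assumed 5% to 20% chance of a Day 6 visit and is not an estimate from the documents. The true count can be read from the recorded visit dates. This is a small error, but worth correcting because the rule gives a wrong result for a subject who followed the schedule.

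**What to change.** In SAP Table 6.7:1, change the Visit 3 window to Days 2-5 and the Visit 4 window to Days 6-11. Keep the safety-lab footnote and leave the start of the first post-baseline window on Day 2. Every compliant day of every Part A visit then falls in its own window, and all 15 combinations of Visit 3 and Visit 4 days fill both visits.

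The cost is two table cells and no new data. The one trade-off is that a Visit 3 held late, on Day 6, would then fall in the Visit 4 window. That visit is outside its own ±1 tolerance, so the change favours the compliant visit. The report could also state how many Part A subjects had Visit 4 on Day 6.
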